6.1.4 Study Data Collection

All study scans will be performed to satisfy one or more aims of the study, as follows:

- 1) **Aim 1:** Perform iterative evaluations of the device (including features, accessories and components) to optimize device performance, assess feasibility of new features, and to perform testing in general support of product and technology development. Aim 1 is to perform evaluations necessary to enable scientists and engineers to establish appropriate design specifications; to optimize the device, accessories, and their various components; and to establish feasibility. Evaluations conducted using investigational devices; devices with regulatory clearance but have not met requirements for commercial release; and devices used off label are included within the scope of this study.
- 2) **Aim 2:** Perform activities to support design validation and/or to confirm user requirements and specifications have been met, as per design controls and other applicable requirements. This includes activities to test that human image quality and system features are acceptable for clinical use and that the system usability meets user needs.
- 3) **Aim 3:** Evaluate device complaints and analyze potential causes. Aim 3 is to reproduce and, when possible, determine root cause of non-safety related complaints (e.g. reports of degraded image quality) that can only be reproduced and investigated in vivo.

Comparator devices (a device used to compare ultrasound against another research device) may be used during the study scans for any aim. Information about the scan (including the resultant images/electronic files, scan aim, date, and relevant parameters of scanning) may be accessed for research purposes.

Study Staff will record information in source documentation about each study scan including:

- Study aim(s) satisfied
- Date of scanning
- Duration of scan exposure
- Device identification (including applicable software versions)
- Anatomical region(s) scanned
- Subject ID#

6.1.5 Subject Follow-Up

AEs will be collected throughout the scan duration (start to conclusion) of the investigational ultrasound exam. AEs unresolved upon completion of the investigational ultrasound exam will be followed until resolution. No other follow-up procedures will be conducted.

6.2 Incidental Finding Notification

The ultrasound procedures performed in this study are not for diagnostic use. The Device Operators may or may not be licensed to interpret the images for potential abnormalities. However, should the Device

Study Title: Development Of Medical Ultrasound Systems, Accessories, And

Components - GE Bangalore

Study Number: 110.08-2015-GES-0004

Operators or Study Staff observe what they interpret to be a potential abnormality, the following procedures will be followed:

- An *Incidental Finding Notification* will be issued to the subject stating that a potential abnormality called an “Incidental Finding” has been observed, and a copy will be placed in the subject’s study file.

All incidental findings will be reported and filed in the subject’s study file, even if the incidental finding was identified during a previous visit.

7. TRAINING PLAN

7.1 GE Facility and Study Staff Roles

Study Staff – Individuals trained on the study protocol and, if necessary, device operation for this study. Records of study staff training will be retained as part of the Sponsor’s Clinical History File (CHF).

The Sponsor may identify non-GEHC employees and other research partners (such as visiting physicians, consultants, Original Equipment Manufacturers (OEM), or other researchers) to provide engineering, clinical domain expertise, and feedback necessary to meet the study aims.

7.2 Training Plan for the Research Device

Device Operators will be provided with appropriate device training or will be qualified based on experience, such as by credentials or work experience in device engineering, clinical imaging, imaging science/physics, or other relevant disciplines. Device Operators may be employees or contractors of GE Healthcare or non-GE employees such as physicians, sonographers, or other researchers. All Device Operators will complete training and/or be qualified prior to being added as Study Staff.

7.3 Device Manuals

Device manuals may be accessed electronically at the Common Documentation Library [REDACTED] or will be made available at the site. Because devices used in this study are under continuous development, manuals may not be available for iterations of a device.

7.4 Training Plan for Protocol

The sponsor will ensure that study staff (including the PI, study staff, and device operators) are trained on the following as necessary for their roles in the study:

- Protocol Training – including training on study procedures and completion of Case Report Forms (CRFs)
- Good Clinical Practice (GCP) for medical devices per ISO 14155:2011
- Study-Specific Informed Consent

A record of training attendance and date conducted will be stored in the Site Regulatory Binder and included in the Sponsor’s Clinical History File (CHF).

Study Title: Development Of Medical Ultrasound Systems, Accessories, And

Components - GE Bangalore

Study Number: 110.08-2015-GES-0004

The PI is responsible for communicating with the Sponsor's Clinical Affairs representatives (Sponsor representative), maintaining the regulatory binder, delegating various study activities (i.e. informed consent, recruitment), ensuring that study staff are trained, ensuring that devices are correctly labeled, and ensuring that the protocol is followed, in accordance with IRB and regulatory requirements.

7.4.1 Observation of Study Scans

In some cases, observation by GE staff or third parties (such as engineers, research partners, or others) is necessary for technical evaluation and development of the devices under study. As authorized by GE Healthcare, observers may be present during scanning with subject approval.

8. DATA REPORTING, ANALYSIS, AND STATISTICS

There is no prospective plan to generate or utilize cohort-based clinical or efficacy data derived from this study for regulatory purposes, and no prospective cohort-based summary of study scan data collection is planned. Individual anonymized sample images may be used for regulatory submission, engineering development, publication and other purposes, as determined by the Sponsor. The Sponsor will generate the final report that summarizes the number and type of study scans, at minimum.

8.1 Data Reporting

A Final Clinical Study Report will be prepared by the Sponsor. This report will contain a report of the primary endpoint, and results from all study data collection activities will be stored at the investigational site (but are not prospectively planned to be summarized as part of the final study report for this study). Data collected from study scans in this study may be used for other engineering activities outside of the clinical report for this study, including activities such as retrospective analyses, meta-analysis, and other activities authorized by GE.

The final clinical report will contain a report of subject disposition and listing of AE/SAE by description, severity, and device relatedness of and unexpected device issues not anticipated based on engineering optimization activities. A summary of device complaints and resolution will be included in the final clinical report for this study. Individual narratives for each SAE and unexpected device issue will be summarized as part of the final report.

8.2 Statistical Analysis Methods

Descriptive statistics may be used to describe enrollment, subject disposition, and other parameters related to study conduct as part of the final clinical report.

8.3 Sample Size Justification

The sample size is not designed to test any statistically powered endpoint and is determined based on the engineering development needs of the Sponsor. Due to the heterogeneous nature of the study procedures, each subject will be allowed to participate multiple times, if he/she remains eligible per protocol requirements. As possible, the minimum number of study scans will be conducted to meet the internal engineering and optimization needs of the Sponsor, and it is prospectively planned that significantly fewer subjects (fewer study scans) than the maximum may be enrolled, if possible to achieve study aims.

Study Title: Development Of Medical Ultrasound Systems, Accessories, And

Components - GE Bangalore

Study Number: 110.08-2015-GES-0004

8.4 Interim Reporting

No interim reporting is prospectively planned as part of this research study; however, the Sponsor may monitor the study and, at its discretion, complete formal interim reporting at any interval it deems necessary.

8.5 Handling of Missing Data

No interim reporting is planned as part of this research study; however, the Sponsor may monitor the study and, at its discretion, complete interim reporting at any interval it deems necessary.

9. SAFETY

9.1 Anticipated Adverse Events and Device Effects

The non-invasive ultrasound devices and their accessories under study share a common and well-understood safety profile.^{19, 25, 26} According to the American Institute of Ultrasound in Medicine (AIUM) Safety in Training and Research (2012) statement, no hazard has been identified that would preclude the prudent and conservative use of such diagnostic ultrasound in research when exposure times and risk conditions are as low as reasonably achievable (ALARA) within the context of the research objectives.²⁵

There are known risks associated with conventional ultrasound scanning. The risks of ultrasound scans performed in this study are not expected to be greater than those encountered in routine clinical practice using diagnostic ultrasound, which include:

- Transient tissue warming induced by acoustic energy used in ultrasound scanning, which can, in rare cases, lead to superficial burns.
- Formation of small pockets of gas in body fluids or tissues (known as “acoustic cavitation”) is a rare effect of ultrasound scanning. Because no contrast agents are used in this study, the likelihood of cavitation is remote.²⁶ The long-term effects of tissue heating and cavitation caused by ultrasound are not known.
- Local discomfort, superficial contact injury, and/or skin irritation due to contact with materials in the transducer, gel, disinfectant, or other device components.
- Direct contact with moving or stationary device components can lead to bruising, abrasions, and/or tears in the skin or, pinching, or in rare cases, more serious injury. Subjects and operators are able to immediately end scans in the event of discomfort.
- While standard cleaning procedures are followed, there is a remote possibility cross-contamination when multiple-use devices or components are used, which can lead to infection or other conditions possibly requiring medical intervention.
- As with any medical electrical equipment, there is a risk of electric shock if subjects or operators come into direct contact with electrically active elements. These risks are mitigated by design in ultrasound devices so that the chance of electrical shock is remote.

These effects are typically not very painful and resolve spontaneously after the scan ends without further medical intervention. Maneuvers during scanning, such as changing clothing, positioning, and/or having a partially full bladder are not expected to cause severe discomfort.

Study Title: Development Of Medical Ultrasound Systems, Accessories, And

Components - GE Bangalore

Study Number: 110.08-2015-GES-0004

While there have been rare reports of chronic or severe bioeffects resulting from ophthalmic scanning (such as cataracts/vision impairment),^{26,27} the additional protections employed to minimize risks to subjects in this study are well within conservative ranges to mitigate the risk of possible serious or chronic effects of ultrasound. Within the scanning parameters set forth in this protocol, serious or chronic injury is not expected to result for any participating subject.

There is always a chance of unexpected risks. Throughout the study, the Sponsor will evaluate and update safety information in study documents.

9.2 Adverse Event Definitions

Adverse Event (AE): any untoward medical occurrence, unintended disease or injury, or untoward clinical signs (including abnormal laboratory findings) in subjects, users or other persons, whether or not related to the investigational medical device [ISO 14155:2011 3.2]. This includes events related to the investigational device or the comparator and to the procedures involved. For users or other persons, this is restricted to events related to the investigational medical device.

Serious Adverse Event (SAE): an adverse event that led to death; led to a serious deterioration in the health of the subject, that either resulted in a life-threatening illness or injury, a permanent impairment of a body structure or a body function, or in-patient or prolonged hospitalization, or medical or surgical intervention to prevent life-threatening illness or injury or permanent impairment to body structure or a body function; or led to fetal distress, fetal death or a congenital abnormality or birth defect. Planned hospitalization for a pre-existing condition, or a procedure required by the protocol without serious deterioration in health, is not considered a SAE [ISO 14155:2011 3.37].

Anticipated: Any adverse event and/or reaction, the specificity or severity of which is consistent with the IRB approved informed consent, protocol, investigator brochure, or product labeling.

Adverse Device Effect (ADE): an adverse event related to the use of an investigational medical device [ISO 14155:2011 3.1]. This includes any adverse events resulting from insufficient or inadequate instructions for use, deployment, implantation, installation, or operation, or any malfunction of the investigational medical device. This includes any event that is a result of a user error or intentional misuse of the investigational device [ISO 14155:2011 3.43].

Serious Adverse Device Effect (SADE): an adverse device effect that has resulted in any of the consequences characteristic of a serious adverse event [ISO 14155:2011 3.36].

Unanticipated serious adverse device effect (USADE): a serious adverse device effect, which by its nature, incidence, severity, or outcome has not been identified in the current version of the risk analysis report [ISO 14155:2011 3.42].

9.3 Monitoring and Recording AEs and USADEs

All adverse events (AE), including all serious adverse events (SAE) and Unanticipated Serious Adverse Device Effects (USADEs), are required to be collected, investigated, and documented during the study reporting period, as defined in the study procedure set forth in this protocol. For the purposes of AE reporting, enrolled subjects will be monitored for AEs during the time between entering the research scanning area at the site for their research scan and the time that they exit the research scanning area. Subjects will not be followed for any potential or existing AEs after leaving the research scanning area, with the exception of SAEs that occur during scanning, which will be followed to resolution.

Study Title: Development Of Medical Ultrasound Systems, Accessories, And

Components - GE Bangalore

Study Number: 110.08-2015-GES-0004

Any AEs will be recorded on the Adverse Event Case Report Form. Documentation will include:

- Description of Event
- Date of onset and resolution
- Severity (mild, moderate, or severe)
 - *Mild:* Symptom(s) barely noticeable to the subject or does not make the subject uncomfortable. The AE does not influence performance or functioning. Prescription drugs are not ordinarily needed for relief of symptom(s).
 - *Moderate:* Symptom(s) of a sufficient severity to make the subject uncomfortable. Performance of daily activities is influenced. Treatment of symptom(s) may be needed.
 - *Severe:* Symptom(s) of a sufficient severity to cause the subject severe discomfort. Treatment for symptom(s) may be given.
- Serious (yes/no)
- Causal relationship to investigational medical device? (not related, possibly related, or related)
 - *Not related:* The adverse event is reasonably expected to be related to (or caused by) a concurrent illness, effect of another device/drug or other cause, and is unlikely related to the investigational product.
 - *Possibly related:* The adverse event is reasonably expected to be related to the investigational product, and an alternative etiology is equally or less likely compared to the potential relationship to investigational product.
 - *Related:* There is a strong relationship to investigational product or recurs on re-challenge, and another etiology is unlikely or there is no other reasonable medical explanation for the event.
- Treatment given and/or action taken (procedure stopped/paused, withdrawn from study, or no action)
- Anticipated (yes/no): Anticipated is defined as events previously observed and documented in the Foreseeable Adverse Events and Adverse Device Effects section.

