3.3.2 Safety Endpoints

The number and type of safety issues, including adverse events (AEs) and serious adverse events (SAEs) will be reported. The number and type of device complaints will be reported.

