5.7 Screening Subjects for Enrollment

Subjects may be pre-screened via telephone or email following IRB/EC-approved scripts to assess potential eligibility.

Informed consent will be obtained as described in the Informed Consent and Privacy Requirements section. Upon agreeing to participate in the Study, the subject will sign and date the ICF. The subject will be assigned an identification code unique to the subject (i.e. next sequential number on the enrollment log). A subject's enrollment in the study begins when he/she completes the above Informed Consent process and is assigned a unique study identification code.

Study Title: Development Of Medical Ultrasound Systems, Accessories, And

Components - GE Bangalore

Study Number: 110.08-2015-GES-0004

After the subject has completed the informed consent process, Study Staff will verify that he or she meets all of the inclusion criteria and none of the exclusion criteria. Determination of eligibility relies on information reported by the subject. The Study Staff may or may not have necessary medical training or licensure to confirm subject self-reported health status and will not make independent assessments.

Subjects may participate more than once throughout the study's duration. Eligibility will be documented at the subject's first visit, and for any subsequent visits it will be confirmed that the subject remains eligible per the inclusion/exclusion criteria prior to the study scan.

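### Planned AE collection ends on site, no step at return visits asks about events in between, and Sections 6.1.5 and 9.3 conflict on window and follow-up

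*Protocol*

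**What the plan says.** Section 9.3 sets the AE window by place: "enrolled subjects will be monitored for AEs during the time between entering the research scanning area at the site for their research scan" and the moment they leave it. It continues: "Subjects will not be followed for any potential or existing AEs after leaving the research scanning area". That sentence makes a single exception: "with the exception of SAEs that occur during scanning, which will be followed to resolution".

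Section 6.1.5 sets the window by the scan itself: "AEs will be collected throughout the scan duration (start to conclusion) of the investigational ultrasound exam". It then says that AEs still unresolved at that point are followed until they resolve, and that there is no other follow-up.

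Section 9.1 names harms that need not show themselves on site. One is cross-contamination through reused components, "which can lead to infection or other conditions possibly requiring medical intervention". It also acknowledges "rare reports of chronic or severe bioeffects resulting from ophthalmic scanning (such as cataracts/vision impairment") and says that the long-term effects of heating and cavitation are unknown.

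Subjects may take part repeatedly. Under Section 5.7, "for any subsequent visits it will be confirmed that the subject remains eligible per the inclusion/exclusion criteria prior to the study scan". Section 6.1 adds that consent must be on the current form. Neither section calls for a history of events since the last scan.

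The safety endpoint in Section 3.3.2 is unqualified: "The number and type of safety issues, including adverse events (AEs) and serious adverse events (SAEs) will be reported". Section 8.1 promises a listing of AEs and SAEs by description, severity and device relatedness, again with no statement that it covers on-site events only.

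**The concern.** The AE window and the risk list do not match. The protocol tells subjects and the ethics committee that certain harms are possible, and some of these would plausibly become apparent only after the subject has gone home. Planned collection has stopped by then, and the next planned contact does not ask about them.

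Two things are at stake. First, a report showing few or no AEs could be read as reassurance about all the risks in Section 9.1, when planned collection covered only the hours on site. Second, Section 9.1 says the sponsor will evaluate and update safety information throughout the study. A non-serious infection after a shared probe, for example, has no planned route into the information that such an update would use. The subject may come back for further scans, some on pre-market devices, without anyone having asked.

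Separately, a site cannot follow Sections 6.1.5 and 9.3 as both are written, so the content of the AE listing depends on which section the staff apply.

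**Working it through.** The protocol gives no figure to reproduce: there is no powered endpoint (Section 8.3) and no expected AE rate. The check is mainly a comparison of the sections.

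**1. The two AE rules side by side**

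| | Section 6.1.5 | Section 9.3 |
|---|---|---|
| Window opens | scan start | entry to the scanning area |
| Window closes | scan conclusion | exit from the scanning area |
| Unresolved non-serious AE | followed to resolution | not followed after exit |
| SAE during scanning | followed to resolution | followed to resolution |
| Event beginning after exit | no planned collection | no planned collection |

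The sections agree only on the last two rows. Section 6.1.3 starts the scan when the device touches the skin and scanning begins. An event while the subject is changing clothes in the area, or in the area after the scan ends, is therefore inside the Section 9.3 window and outside that of Section 6.1.5.

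**2. Length of the window**

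Section 6.1.3 allows up to 5 scans a day of up to 60 cumulative minutes, with breaks of about 15 minutes between them:

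5 × 60 + 4 × 15 = 360 minutes = 6 hours.

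Pauses and waiting can lengthen the stay, but planned collection still ends the same day.

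**3. Routes by which a later event could be recorded**

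- Section 9.2 defines an AE with no limit on time of onset, and the AE form in Section 9.3 takes a date of onset.
- A returning subject is inside the Section 9.3 window again on entering the area, so an event that persists could be noted.
- Section 9.4 makes SAEs and USADEs reportable within 72 hours of knowledge of the event, wherever it began.
- Section 9.5 lets staff report a device issue that they suspect poses a safety risk. Complaints count in Section 3.3.2 and are summarised under Section 8.1.

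None of these is an active question. Each depends on the subject volunteering the event, on its still being evident, or on staff suspecting the device. The Section 9.4 trigger does not cover non-serious events.

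**4. What incomplete capture does to a count (illustration only)**

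Let p be the per-subject risk of a harm and c the probability that an occurrence is recorded. Neither is in the protocol; both are assumed. With the maximum of 150 subjects (Section 5.2), the chance of recording at least one event is 1 − (1 − p·c)^150.

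| p | c = 1 | c = 0.25 | c = 0.10 |
|---|---|---|---|
| 0.5% | 53% | 17% | 7% |
| 1% | 78% | 31% | 14% |
| 2% | 95% | 53% | 26% |

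If 0 of 150 subjects had a recorded event, the one-sided 95% upper bound would be 1 − 0.05^(1/150) = 2.0%. That bound would apply only to harms that become apparent while the subject is on site.

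**The case against.** The strongest reply is that the window is stated openly and suits the study. The design is descriptive and plans no cohort-based safety analysis (Sections 3.1, 4.1 and 4.2). Section 8.1 promises a listing, not a rate. Section 9.1 calls infection a remote possibility, says the listed effects typically resolve on their own after the scan, and does not expect serious or chronic injury. Eye scanning is capped at 15 cumulative minutes per eye per day (Section 6.1.3). The return check also has health content: exclusion criterion 3 removes anyone whom staff think would be put at additional risk, and Section 6.1 lets staff limit visits.

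Much of this stands, and it keeps the point modest. It does not remove it. An expectation that no chronic injury will occur cannot be checked by a window that closes at exit. Eligibility relies on what the subject reports, so an event that nobody asks about may not inform that check either. A descriptive endpoint still needs a label that matches what was collected.

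A reader might go further and infer that late harms cannot enter the safety endpoint at all, so that their count is zero by design. The protocol does not support that. It is silent about such events rather than prohibitive, and the routes in step 3 of the working remain open. Nor does the protocol give onset times: that infection or vision effects would appear after exit is a plausible inference, not something it states.

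**Conclusion.** The point holds as a gap in systematic collection. Active AE ascertainment ends on the day of the scan under either section, return visits include no interval history, and Sections 3.3.2 and 8.1 do not tell the reader so.

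The number of events missed cannot be estimated. The protocol gives no onset times, no event rates and no frequency of return visits, and the table in the working shows only the direction and possible scale under assumed values. No planned inference or stated conclusion depends on these events, so the consequence is confined to how complete the AE listing is and how it will be read.

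The conflict between Sections 6.1.5 and 9.3, on the window and on follow-up of unresolved non-serious AEs, needs no assumption. It is visible in the text and must be resolved whatever is decided about later events.

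**What to change.** **(a) Collect or label.** In both Section 9.3 and Section 6.1.5, add to the existing return-visit eligibility check one question about any event since the last scan. Record the answers on the AE form, together with any event that a subject reports spontaneously after leaving and that staff consider possibly related or related. List these apart from on-site events, so that actively monitored and recalled events are not mixed. If this is not adopted, state in Sections 3.3.2 and 8.1 that the AE counts cover on-site events only.

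**(b) Reconcile.** Bring Sections 6.1.5 and 9.3 to one AE window and one rule on unresolved non-serious AEs. Which rule to adopt is for the sponsor and investigator. Changing Section 9.3 alone would leave Section 6.1.5, which rules out other follow-up, contradicting it.

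**Cost.** One question at a visit already being held, a few sentences of text, and one further listing; no extra visits. Some unrelated events will be recorded and recall will be imperfect. The period after each subject's last visit, which for single-visit subjects is everything after exit, stays uncovered apart from spontaneous reports. The labelling alternative needs only a wording change, but it collects nothing more.

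### Sections 6.1.5 and 9.3 give opposite follow-up instructions for a non-serious AE that arises during a scan and is still unresolved when the subject leaves

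*Protocol*

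**What the plan says.** **Follow-up.** Section 6.1.5 (Subject Follow-Up) states: "AEs unresolved upon completion of the investigational ultrasound exam will be followed until resolution". It makes no distinction by seriousness. Section 9.3 (Monitoring and Recording AEs and USADEs) states: "Subjects will not be followed for any potential or existing AEs after leaving the research scanning area". The only exception it makes is for SAEs whose onset falls within scanning; those are to be followed until they resolve.

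**Collection window.** Section 6.1.5 states: "AEs will be collected throughout the scan duration (start to conclusion) of the investigational ultrasound exam". The synopsis (Procedures/Methods) likewise ties AE monitoring to the research scan. Section 9.3 first requires events to be documented "during the study reporting period, as defined in the study procedure set forth in this protocol", and then sets monitoring for AE reporting as "the time between entering the research scanning area at the site for their research scan and the time that they exit the research scanning area".

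**What is recorded and reported.** The AE form described in 9.3 asks, for any AE, for "Date of onset and resolution". Section 3.3.2 makes the number and type of AEs and SAEs a safety endpoint. Section 8.1 has the final report list them by description, severity and device relatedness.

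**The concern.** These are operating instructions for study staff, and on one class of event they point in opposite directions. Section 10.3 counts any failure to follow a protocol requirement as a deviation, so staff who meet this event deviate from one section whichever way they act.

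Two things are at stake for that class:

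- **The AE record.** If 9.3 is followed, the resolution date cannot be obtained for an event still open at exit.
- **The subject.** If 9.3 is followed, nobody is due to look again at a non-serious event that worsens after the subject leaves. Under 6.1.5 somebody is.

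Safety events and device complaints are the only endpoints besides the number and type of scans (Section 3.3), so a clear rule for AEs matters even in a purely descriptive study.

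**Working it through.** The plan gives no figure to reproduce and no arithmetic applies. The check sets the two sections side by side, case by case.

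| Event | Section 6.1.5 | Section 9.3 | Result |
|---|---|---|---|
| Non-serious AE, onset during a scan, resolved before exit | Follow to resolution, which happens on site | Monitor until exit | Both can be obeyed |
| Non-serious AE, onset during a scan, unresolved at exit | Follow to resolution | Do not follow after exit | **Contradiction** |
| SAE, onset during a scan, unresolved at exit | Follow to resolution | Follow to resolution | Agree |
| Non-serious AE, onset after the last scan and before exit, unresolved at exit | Trigger not met, because the event was not present when the exam was completed | Collect, but do not follow after exit | No contradiction; only the window wording differs |

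**Can the second row be read away?** Three routes were tried.

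1. *Is 9.3 silent on non-serious AEs?* No. It covers any AE and then makes an exception for certain SAEs, so non-serious AEs stay under the prohibition.
2. *Does 9.3 address only new events after exit?* No. It names existing events as well as potential ones.
3. *Does another section settle precedence?* No. Section 9.4 lets the sponsor ask for further follow-up information but sets no follow-up rule. Section 9.6 deals with cases needing transfer from the scanning area to hospital.

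**Can the second row occur?** Yes. Section 9.1 lists superficial burns (rare), bruising, abrasions, skin tears and skin irritation among the known risks. It says that the effects typically clear by themselves once the scan has ended. That wording places resolution after the scan, allows for exceptions, and does not say whether resolution comes before or after exit.

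**Window.** Section 6.1.3 starts a scan at skin contact and stops it when the scan is complete. The period named in 6.1.5 therefore lies inside the entry-to-exit period of 9.3. Section 6.1.5 does not say that AEs are collected only during the scan, so staff who monitor from entry to exit satisfy both sections.

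**The case against.** **The events are minor and short-lived.** Section 9.1 expects the known effects to be mild and to pass without treatment, and SAEs during scanning are followed under both sections. This stands as a limit on size. It does not tell staff what to do with an event that is still open at exit.

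**Section 9.3 may be the intended rule.** The Rev 2.0 entry in the version table lists 9.3 to 9.5, and not 6.1.5, as the sections where AE monitoring, recording and reporting were clarified. That suggests, without proving, that 9.3 is the deliberate rule and 6.1.5 was left behind. The point is fair, and for that reason aligning 6.1.5 to 9.3 is offered as an alternative fix. The current text still contains both rules.

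**Stronger readings that the documents do not support:**

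- *The collection windows contradict each other.* A reader might infer this, and infer that the AE count in 3.3.2 is undefined. That follows only if 6.1.5 is read as excluding everything outside the scan, which it does not say. The windows are nested. The difference is an inconsistency of wording, made worse by 9.3 first deferring to a period defined elsewhere and then giving its own.
- *Some SAEs go without follow-up because the 9.3 exception is limited to those during scanning.* That phrase is not defined. If it means the whole visit, no gap exists. On the narrow reading, 6.1.5 and 9.6 still cover most cases. This is not a finding.
- *Severity grades in the final report would be wrong.* The moderate grade does refer to effects on daily life ("Performance of daily activities is influenced"), but it also rests on discomfort, which can be judged on site. That a grade would change after exit is conjecture.

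**Conclusion.** The contradiction is real and confined to one class of event: non-serious AEs that begin during a scan and remain unresolved when the subject leaves the scanning area. For that class, 6.1.5 requires follow-up and 9.3 rules it out.

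The number of such events cannot be computed, because the protocol gives neither AE rates nor times to resolution. With the risk profile in 9.1 and at most 150 subjects it is probably small, though subjects may return for repeated scans. That is a judgement and not a calculation.

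No inference is affected: Section 3.1 rules out hypothesis tests and cohort-based inference. The damage is to the completeness of the AE record and to the care of the few subjects concerned. The conclusion rests on the plain wording of the two sections and on the absence of any precedence rule. The change should be made, because the instructions cannot both be obeyed and the repair is cheap.

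**What to change.** **Preferred.** Amend 9.3 so that any AE, serious or not, with onset between entry to and exit from the research scanning area and unresolved at exit is followed to resolution. Section 6.1.5 already requires this for AEs unresolved at the end of the exam. The cost is a changed sentence in 9.3 and a few extra follow-up contacts. These should be easy to make, since subjects are GE employees or contractors at the facility (Section 5.4).

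**Alternative.** If the sponsor intends the 9.3 rule for non-serious AEs, amend 6.1.5 to match and record events still open when the subject leaves as ongoing at exit. This needs no extra contacts but may need a change to the AE form. It also accepts that worsening after exit will not be sought.

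**Wording alignment under either option.** State the entry-to-exit window of 9.3 in 6.1.5 and in the synopsis (Procedures/Methods), both of which now refer only to the scan. Delete the clause in 9.3 that defers to the study procedure for the reporting period. This costs a few words in three places.
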